6.16.2 Eliciting and Reporting AEs

The investigator will periodically assess subjects for the occurrence of AEs after a subject consents to participation in the study. To avoid bias in collecting information about AEs, the investigator should ask subjects the following question: "How have you felt since you were last checked?" All AEs (serious and non-serious) reported by the subject must be recorded on the source documents and CRFs provided by the sponsor.

It is the investigators responsibility to review the results of all laboratory tests as they become available. For each abnormal laboratory test result the investigator needs to ascertain if this is a clinically significant change from baseline for that individual subject (this determination, however, does not necessarily need to be made the first time an abnormal value is observed. The investigator may repeat the laboratory test or request additional tests to verify the results of the original laboratory tests). If the laboratory value is determined to be a clinically significant and abnormal change from baseline for that subject, this is considered a laboratory AE.

Hypoglycemia is defined as any FPG or SMBG value <70 mg/dL and documented as described in [Section 6.16.11](#).

Any increase in liver function tests (AST, ALT, or bilirubin) greater than 3 times the ULN for the laboratory utilized will be considered a laboratory AE.

In addition, the sponsors Medical Monitor or its designated personnel must be notified immediately by telephone, email, or fax of any immediately reportable AEs (IRAE) according to the procedure outlined below. Special attention should be paid to recording hospitalization and concomitant medications.

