6.16.10 Hepatotoxicity

If plasma AST and/or ALT concentrations $> 3 \times$ ULN are detected, the investigator will record in the source documents the date corresponding to the date of the laboratory abnormality; the type, frequency, and dose of any concurrent medications or supplements taken by the subject within the 14 days of the detected abnormality; and any symptoms or change in physical exam that have occurred since the prior assessment. The investigator should perform additional laboratory and imaging tests to attempt to establish the cause of the AST and ALT elevations, including ruling out any potential contribution from bone or muscle etiologies.

Any clinically significant increase in hepatic enzymes and specifically any ALT or AST $> 3 \times$ ULN requires immediate repeat test within 48 to 72 hour to confirm the hepatic enzyme elevation and should be repeated based on the clinical situation at least every 96 hour (4 days) until ALT and AST return to $< 2.5 \times$ ULN. Study medication should be stopped and the event should be reported as a laboratory AE within the CRF if the enzyme elevation is confirmed or worsening.

Hepatotoxicity will be diagnosed and entered as an AE should any of the following occur:

- ALT or AST > 8 x ULN;
- ALT or AST > 3 x ULN and total bilirubin > 2 x ULN or INR > 1.5
- ALT or AST > 3 x ULN with the appearance of fatigue, nausea, vomiting, right upper quadrant pain or tenderness, fever, rash, and/or eosinophilia (> 5%).

In the event of hepatotoxicity, investigational product should be permanently discontinued. The investigator is encouraged to consult with the Medical Monitor regarding diagnostic evaluation for the hepatic enzyme elevations. Consultation with a hepatologist may also be appropriate in some circumstances.

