9.3.3. AE of Special Interest

AE of special interest include UTI, GMI, diuretic effects, hepatotoxicity, MACE, hypoglycemia, fracture, malignancy, hypersensitivity reactions, hypotensive episodes, acid base disorders, DKA, renal failure events, and amputations. The AEs of special interest, except for MACE and amputations, will be prospectively identified based on the MedDRA PTs in the AEs log by a medical expert prior to the data base lock and unblinding of the individual subject treatment assignment. The list of AEs of special interest will be confirmed in a peer review process. Adjudicated MACE will be summarized in the same AE of special interest table. Hypoglycemia events by severity, and amputations will be summarized separately. Additional information will be collected for DKA. These data will be listed if available.

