laboratory reports so the sponsor, investigators, study coordinators, pharmacists, study subjects, and the CEC members will remain blinded to the dosing assignment.

The baseline value will be the latest value obtained on or prior to Day 1. Change from baseline for all continuous parameters will be calculated as the post-baseline value minus the baseline value.

Data summaries will use descriptive statistics (number of subjects [n], mean, standard deviation [SD], median, minimum and maximum) for continuous variables, and frequency and percentage of subjects for categorical and ordinal variables

Observed values (in SI units) and change from baseline over time will be summarized by treatment group. Laboratory data will be classified as low, normal, or high relative to the parameter's reference range. Laboratory abnormalities for each treatment will also be summarized with shift tables for selected parameters.

All laboratory data will be listed. For hematology, chemistry, including serum lipids, columns will be included for normal ranges and individual abnormal laboratory values will be flagged and clinical significance will be indicated. Listing for urinalysis will include the microscopic examination provided for subjects who have a positive result from the urinalysis dipstick evaluation.

Table 4 List of Laboratory Tests

Test Name	Blood or Urine Vol. (mL)	Shipment
Hematology	2 (blood)	Ambient
-Hematocrit (Hct)	-Mean corpuscular volume (MCV)	
-Hemoglobin (Hgb)	-Red cell distribution width (RDW)	
-Mean corpuscular hemoglobin (MCH)	-Red blood cell (RBC) count	
-Mean corpuscular hemoglobin concentration (MCHC)	-White blood cell (WBC) count with differential	
-Platelet count		
Serum Chemistry and Electrolytes	10 (serum)	Ambient
-Albumin (ALB)	-Calcium (Ca)	
-Alanine aminotransferase (ALT)	-Magnesium	
-Aspartate aminotransferase (AST)	-Phosphorus	
-Blood urea nitrogen (BUN)	-Potassium (K)	
-Glucose	-Sodium (Na)	
-Bicarbonate (HCO ₃)	-Total bilirubin	
-Creatinine	-Direct bilirubin	
-Chloride (Cl)	-Uric acid	
-Total protein		
Glycemic Control		Ambient
-Fasting plasma glucose (FPG)	2 (plasma)	
-Hemoglobin A1c (HbA1c)	2 (blood)	
Serum Lipids	6 (serum)	Ambient
-Total cholesterol (TC)	-Low-density lipoprotein cholesterol (LDL-C), calculated	
-High-density lipoprotein cholesterol (HDL-C)	-LDL-C, direct (if applicable)	
-Triglycerides (TG)		
Urinalysis	10 (urine)	Ambient
-Appearance	-Nitrite	
-Bilirubin	-Occult blood	
-Color	-pH	
-Glucose	-Protein	

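### Protocol 6.16.2 and 6.16.10 give different AE triggers for an unconfirmed ALT or AST above 3 x ULN, and no planned summary counts subjects by arm on the protocol's own ALT/AST and bilirubin limits

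*Protocol*

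**What the plan says.** **Reporting.** Protocol 6.16.2 (Eliciting and Reporting AEs) sets a trigger for laboratory AEs: "Any increase in liver function tests (AST, ALT, or bilirubin) greater than 3 times the ULN for the laboratory utilized will be considered" one of these. No repeat test is mentioned in that sentence. Protocol 6.16.10 (Hepatotoxicity) requires a repeat test within 48 to 72 hours for ALT or AST above 3 x ULN, and then says that "the event should be reported as a laboratory AE within the CRF if the enzyme elevation is confirmed or worsening".

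**Hepatotoxicity.** Protocol 6.16.10 goes on to have hepatotoxicity diagnosed and entered as an AE if any one of three criteria is met:
- a value of either enzyme above 8 x ULN
- the combined criterion, "ALT or AST > 3 x ULN and total bilirubin > 2 x ULN or INR > 1.5"
- a value of either enzyme above 3 x ULN together with listed symptoms or signs, or with eosinophilia above 5%

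This instruction carries no confirmation condition.

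**Analysis.** SAP 9.3.3 says that AEs of special interest, other than MACE and amputations, "will be prospectively identified based on the MedDRA PTs in the AEs log" by a medical expert before unblinding. SAP 9.4 says: "Laboratory data will be classified as low, normal, or high relative to" the reference range, with shift tables for selected parameters that are not named. All laboratory values are listed. The index of tables (SAP 17) has a chemistry summary by visit (14.3.4.3) and a chemistry shift table (14.3.4.4). No table title refers to multiples of ULN or to ALT/AST and bilirubin in combination.

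**The concern.** Two matters are joined here.

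First, one section makes an AE of a single value above 3 x ULN, while the other makes the report depend on the repeat. Where the two give different answers, sites can record the same laboratory finding differently, and the count of enzyme-elevation AEs by arm then partly reflects site practice.

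Second, the protocol defines hepatotoxicity mostly by numeric limits, yet the SAP never applies those limits to the data. The preferred-term count depends on what sites entered and on which terms the expert selected. The shift tables place every value above the reference range in one class. The SAP treats other events of special interest with numeric definitions differently: hypoglycemia is tabulated by glucose-based category (9.3.3.2) and acute kidney events by stage (9.3.3.4). Protocol 9.8.2 also leaves it to the SAP to specify additional analyses of safety parameters linked to these events. For the liver the SAP specifies none.

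**Working it through.** The plan states no figure on this point, so there is nothing to reproduce. The check sets the rules and the outputs side by side.

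**Step 1: the rules as logic.** All values are multiples of ULN, and ALT stands for ALT or AST.
- R1 (6.16.2): ALT > 3, or bilirubin > 3.
- R2 (6.16.10, laboratory AE): ALT > 3, and confirmed or worsening.
- H (6.16.10, hepatotoxicity AE): ALT > 8; or ALT > 3 with (bilirubin > 2 or INR > 1.5); or ALT > 3 with listed symptoms or eosinophilia.

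**Step 2: where they differ.** A constructed grid tests the logic; its values are assumptions and not event rates. It crosses peak ALT 1.2, 2.5, 3.5, 9; bilirubin 0.8, 1.5, 2.5, 3.5; confirmed or not; INR > 1.5 or not; symptoms or not. That gives 4 × 4 × 2 × 2 × 2 = 128 profiles.
- R1 and R2 differ when ALT > 3 is unconfirmed (2 × 4 × 2 × 2 = 32 profiles), or when bilirubin is 3.5 with ALT ≤ 3 (2 × 1 × 2 × 2 × 2 = 16). The total is 48.
- Of the 32, all 16 with ALT 9 meet H. Of the 16 with ALT 3.5, only those with bilirubin 0.8 or 1.5, INR not raised and no symptoms fail H, which is 2; the other 14 meet it. So 16 + 14 = 30 are AEs under 6.16.10 anyway.
- The 16 isolated-bilirubin profiles are not a contradiction. The 6.16.10 reporting sentence concerns hepatic enzymes and is silent on bilirubin alone, so 6.16.2 applies.
- What remains is 48 − 30 − 16 = 2 profiles. Both are an unconfirmed ALT of 3.5 with bilirubin ≤ 2, INR ≤ 1.5 and no symptoms.

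**Step 3: what the shift classes show.** Assume INR is not raised and there are no symptoms.

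| Peak ALT | Bilirubin | Protocol 6.16.10 criterion | Shift class |
|---|---|---|---|
| 1.2 | 0.8 | none | ALT high, bilirubin normal |
| 3.5 | 0.8 | none (repeat test required) | ALT high, bilirubin normal |
| 9 | 0.8 | ALT > 8 | ALT high, bilirubin normal |
| 1.2 | 1.5 | none | both high |
| 3.5 | 2.5 | ALT > 3 with bilirubin > 2 | both high |

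The first three rows cannot be told apart, nor can the last two. A shift table for each parameter also loses the within-subject pairing that the second criterion needs.

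**Step 4: the other outputs.**
- Table 14.3.4.3 gives a maximum for each parameter and visit. SAP 6.1 and 6.4 put one selected record per visit window into summary tables, so the maximum covers selected records only. It describes one value and does not count subjects.
- Table 14.3.1.9 counts hepatotoxicity from preferred terms. It does not show which criterion was met and cannot find a case that a site did not enter.
- Listing 16.2.8.2 holds the individual values, without a by-arm count.

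**The case against.** The strongest reply is that 6.16.10 already secures the important cases. A subject who meets any of the three criteria must be entered as a hepatotoxicity AE and permanently discontinued from investigational product. If treatment-emergent, that event reaches the TEAE tables and, once product is stopped, the table of events leading to discontinuation (14.3.1.7). This is correct, and it limits the point in three ways.

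- A reader might infer that the hepatotoxicity count as a whole depends on which reporting sentence a site follows. The documents do not support that: protocol-defined cases are AEs under both sections. It could matter to that count only if the expert also assigns lone enzyme-increase terms to hepatotoxicity, and the SAP text gives no term list.
- A reader might infer that a subject with ALT above 3 x ULN and bilirubin above 2 x ULN could be missing from every summary table. Under the plan as written that subject is entered as an AE. Absence from the AE tables would require a site to depart from the protocol, and the values would still be classed as high in any shift table that covers these parameters.
- A reader might want a number of affected subjects. The documents give no rate of elevation or of non-confirmation, and entry excludes ALT or AST above 2.5 x ULN, so no case count can be defended.

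It can also be said that the data are all listed, that a 10 x ULN value selected for a visit would appear as the maximum, and that the table shells are a separate attachment not available here. The first two are true, but neither gives a count of subjects by arm. The third is a real limit: the finding on outputs rests on the SAP text and table titles.

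Finally, 6.16.2 lets the investigator repeat a test before judging clinical significance. That does not remove the conflict, because the sentence on 3 x ULN stands apart and is unconditional.

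**Conclusion.** The point holds in a limited form. The AE-reporting conflict is real but narrow: an unconfirmed ALT or AST above 3 and up to 8 x ULN, with bilirubin at most 2 x ULN, INR at most 1.5 and none of the listed symptoms or eosinophilia. That is 2 of the 128 constructed profiles, which describes the logic and says nothing about frequency. It assumes that the second criterion means ALT or AST above 3 x ULN together with either raised bilirubin or raised INR.

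The analysis gap is separate and does not depend on that conflict. The plan has no prespecified by-arm count on the protocol's ALT/AST and bilirubin limits, and so no check of the site-reported hepatotoxicity count against the laboratory record. What is missing is a summary; the ALT, AST and bilirubin data are collected. The efficacy conclusions are untouched. This is an inexpensive improvement to the safety reporting of a named event of special interest.

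**What to change.** 1. Reconcile the AE-reporting sentences in Protocol 6.16.2 and 6.16.10 so that one trigger applies to ALT or AST above 3 x ULN. Which trigger applies is for the sponsor to decide.
2. In SAP 9.4 add a table by arm, from all scheduled and unscheduled post-baseline results, of the number and percentage of subjects with ALT or AST > 3 x ULN; > 8 x ULN; and > 3 x ULN with total bilirubin > 2 x ULN. Use the ULN of the laboratory that ran each test, and state how close in time the paired ALT/AST and bilirubin results must be. Add a listing of the subjects counted.
3. State that the table does not cover the INR part of the second criterion or the symptom/eosinophilia criterion. INR is in neither document's laboratory list, and symptoms come from AE data. The white-cell differential could supply eosinophils, but that is only part of the criterion.

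The cost is one protocol clarification, one table and one listing, with no new data collection. It should be specified before unblinding.

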6.16.3 Immediately Reportable AEs

The investigator must report any SAE to the sponsor or its representative immediately after the investigator becomes aware of the event. An SAE form should be completed and sent to the sponsor within 24 hours of knowledge of the event.

Non-serious events that require discontinuation of investigational product (including laboratory abnormalities) should be reported to the sponsor within 3 working days. The CRF AE form should be completed and sent to the sponsor.

Subjects experiencing an SAE should be followed clinically until their health has returned to baseline status or no further improvement in condition can be expected with further care. It is expected that the investigator will provide or arrange appropriate supportive care for the subject.

6.16.4 Pregnancy

WOCBP who are sexually active must use an effective method of birth control during the course of the study, in a manner such that risk of failure is minimized. Acceptable birth control methods include, but are not limited to, oral contraceptives, intrauterine devices, Depo-Provera[®], Norplant[®], hormonal contraceptive implants, bilateral tubal ligation, partner with vasectomy, condom or diaphragm plus contraceptive sponge, foam, or jelly, and abstinence.

Before enrolling WOCBP in this clinical trial, investigators must review guidelines about study participation for WOCBP. The topics should generally include:

- General information
- Informed consent form
- Pregnancy prevention information
- Drug interactions with hormonal contraceptives.
- Contraceptives in current use.
- Guidelines for the follow-up of a reported pregnancy.

Prior to study enrollment, WOCBP must be advised of the importance of avoiding pregnancy during trial participation and the potential risk factors for an unintentional pregnancy. The subject must sign an informed consent form stating the above-mentioned risk factors and that the consequences were discussed with her.

During the study, all WOCBP should be instructed to contact the investigator immediately if they suspect they might be pregnant (e.g. missed or late menstrual cycle).

If a subject or investigator suspects that the subject may be pregnant prior to investigational product administration, the investigational product administration must be withheld until the results of serum pregnancy tests are available. If the pregnancy is confirmed, the subject must not receive the investigational product and must not be enrolled or remain in the study. If pregnancy is suspected while the subject is receiving study treatment, the investigational product must be withheld immediately until the result of the pregnancy test is known. If pregnancy is confirmed, the investigational product will be permanently discontinued and the subject will be withdrawn from the trial. (Exceptions to study discontinuation may be considered for life-threatening conditions only after consultations with a sponsor Medical Monitor or designated personnel.) The investigator must notify the Medical Monitor within 3 working days of any female subject who becomes pregnant. This reporting requirement will continue until 4 weeks after the last investigational product exposure.

The investigator must record the event on the Pregnancy Surveillance Form and forward it to sponsor's clinical or designated personnel.

Protocol required procedures for study discontinuation and follow-up must be performed on the subject unless contraindicated by pregnancy (*e.g.*, x-ray studies). Other appropriate pregnancy follow-up procedures should be considered if indicated. In addition, the investigator must report to the sponsor, on the appropriate Pregnancy Surveillance Form, any follow-up information regarding the course of the pregnancy, including perinatal and neonatal outcome. Infants will be followed for a minimum of six months.

6.16.5 Procedure for Breaking the Blind

As indicated in [Section 5.5](#) above, the sponsor, medical monitor, study coordinators, pharmacists, study subjects, and the CEC members will be blinded to the treatment assignment during the study period. The investigator should also remain blinded to the subject treatment during the entire study unless knowledge of the subject's treatment is required for clinical care and safety. The Emergency Code Break module in the IWRS is used for such situations. The investigator must confirm the intention to unblind the subject's treatment to obtain the dose information in IWRS. Upon completion of the unblinding, the system will send an alert to designated study team members that an unblinding event has occurred. Documentation of breaking the blind should be recorded in the subject's medical record with the date and time the blind was broken, and the names of the personnel requesting and authorizing unblinding. The treatment assignment will continue to be withheld from the CEC members until all phase 3 studies are completed.

6.16.6 Follow-up of Non-Serious AEs

Non-serious AEs that are identified on the last scheduled contact must be recorded in the AE CRF with the current status noted. All non-serious events that are ongoing at the time will be recorded as ongoing in the CRF.

6.16.7 Follow-up of Post-Study SAEs

SAEs that are identified on the last scheduled contact must be recorded on the AE CRF page and reported to the sponsor according to the reporting procedures outlined in [Section 6.16.3](#). These may include unresolved previously reported SAEs, or new SAEs. The investigator should follow these SAEs until the events are resolved, or the subject is lost to follow-up. Resolution means the subject has returned to the baseline state of health, or the investigator does not expect any further improvement or worsening of the subject's condition. The investigator should continue to report any significant follow-up information to the sponsor until the event has been resolved.

Any new SAEs reported by the subject to the investigator that occur after the last scheduled contact, and are determined by the investigator to be reasonably associated with the use of the investigational product, should be reported to the sponsor or designated personnel. This may include SAEs that are captured on follow-up telephone contact or at any other time point after the defined study period (*i.e.*, up to last scheduled contact). The investigator should follow SAEs identified after the last scheduled contact until the events are resolved, or the subject is lost to follow-up. The investigator should continue to report any significant follow-

up information to the sponsor until the event has been resolved. This study requires that subjects be actively monitored for SAEs for at least 4 weeks after the last treatment.

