6.17 Concomitant Medication Assessments

A concomitant medication is any medication that the subject has been taking prior to enrollment and that the subject is expected to continue to take for some portion of the trial, as well as any medication other than the investigational product that the subject takes during the course of the trial.

The medications or treatment for controlling hypoglycemia must be recorded as concomitant medications in the CRF. Any medication given to treat hyperglycemia and continued for more than 2 weeks is considered a rescue therapy and should be recorded in the concomitant medication log.

Changes from baseline anti-hypertensive therapy and their rationale must be recorded in the CRF.

All prescription and over-the-counter medications, including vitamins and herbal supplements, that subjects receive during the trial must be documented on the CRF. This documentation should continue until the subjects complete the study.

Insulin and its route of administration will be recorded as total daily dose.

Concomitant medications will be coded using the World Health Organization Drug Dictionary (WHO-DD). A table of concomitant medications based on the Anatomic

Therapeutic Chemical (ATC) classification code and preferred name will be produced. A listing of concomitant medications will include all medications taken by any subjects during the course of the study.

6.18 Removal of Patients from the Trial or Discontinuation of Investigational Product Administration

The investigator must emphasize to potential subjects the importance of continued participation for the full duration of the trial during the informed consent process. Potential subjects should be informed that the trial procedures will allow additional medications to control hyperglycemia or other adverse conditions. It is also important to emphasize that missing data and missed visits could affect the entire trial. If subjects are dissatisfied with the conduct of the trial but have not withdrawn, the investigator should make an effort to address their concerns and retain them in the trial if possible. In doing so, investigators must be careful that the efforts do not cross over into coercion. Investigator should encourage a subject to remain in the study even if the investigational product administration is stopped so that safety information can be collected.

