9.3. ADVERSE EVENTS

Adverse events will be collected and recorded from the time a subject signs the informed consent form (ICF) to the last scheduled contact. And new SAE reported by the subject to the investigator that occur after the last scheduled contact, and are determined by the investigator to be reasonably associated with the use of the investigational product, should be reported to the sponsor or designated personnel. This may include SAEs that are captured on follow-up telephone contact or at any other time point after the defined study period (i.e., up to last scheduled contact). The investigator should follow SAEs identified after the last scheduled contact until the events are resolved, or the subject is lost to follow-up. The investigator should continue to report any significant follow-up information to the sponsor until the event

has been resolved. This study requires that subjects be actively monitored for SAEs for at least 4 weeks after the last treatment.

For all AEs, preferred AE terms and system organ class (SOC) will be coded using terminology from the Medical Dictionary for Regulatory Activities (MedDRA), version 19.0 or higher.

A treatment-emergent adverse event (TEAE) is defined as an AE that begins after the first administration of double-blind study medication or existing AEs that worsen after the first dose of double-blind study medication. All reported AEs will be listed, but only TEAEs will be summarized in tables.

Drug-related AEs will be considered those to be possibly, probably and definitely related to IP administration based on the investigators assessment.

Unless otherwise specified, AEs will be summarized by SOC and PT, with SOC and PTs within SOC presented in descending order of subject incidence.

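### Active SAE monitoring is required for at least four weeks after the last dose, but the last scheduled contact falls nominally at two weeks

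*Protocol*

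**What the plan says.** **The requirement.** Protocol 6.16.7 ends with: "This study requires that subjects be actively monitored for SAEs for at least 4 weeks after the last treatment". SAP 9.3 carries the same sentence.

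**The collection period.** SAP 9.3 opens with: "Adverse events will be collected and recorded from the time a subject signs the informed consent form (ICF) to the last scheduled contact". For the time after that contact, Protocol 6.16.7 and SAP 9.3 describe new SAEs that the subject brings to the investigator and that "are determined by the investigator to be reasonably associated with the use of the investigational product". Protocol 6.16.7 adds: "This may include SAEs that are captured on follow-up telephone contact or at any other time point after the defined study period". Protocol 6.16.3 sets a wider rule, with no relatedness condition and no end date: "The investigator must report any SAE to the sponsor or its representative immediately after the investigator becomes aware of the event".

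**The schedule.**
- Protocol 5.11 makes V8 (week 24) the last day of dosing.
- Protocol 3.2.3 and SAP 3.5 place the exit visit at week 26, or two weeks after the last dose for a subject who terminates before week 24. Protocol 7.10 gives the same two weeks for withdrawal of consent.
- Protocol Appendix 1 and SAP Table 1 both end with V9 at week 26.
- Protocol section 7 allows ±3 days on every visit except V3.
- Protocol 3.4 gives 30 weeks from screening to follow-up.

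**The concern.** Both documents state a minimum period of active safety follow-up that is twice as long as the scheduled follow-up. A site that keeps every visit on time still does not meet 6.16.7, and nothing in the schedule tells it what else to do.

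What is at stake is the completeness of SAE ascertainment in roughly the second half of the stated four weeks. In those days a new SAE is found only if the subject volunteers it or an unscheduled contact happens to pick it up. The text is also unclear on what must then be reported: related events only (the post-contact wording in 6.16.7 and SAP 9.3), or any SAE that comes to the investigator's notice (6.16.3). A study report that repeated the four-week statement would describe monitoring that the schedule did not provide for.

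**Working it through.** **1. Reproduce the stated duration.** Screening is up to 3 weeks (Protocol 7.1), run-in 1 week and treatment 24 weeks (Synopsis), and V9 comes 2 weeks after V8 (Appendix 1):

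3 + 1 + 24 + 2 = 30 weeks.

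This matches Protocol 3.4. The two-week post-dose period is thus the design itself, not a slip in one table. Four weeks after the last dose would need 3 + 1 + 24 + 4 = 32 weeks.

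**2. Scheduled contact after the last dose.** Counting from randomization, week 24 is day 168 and week 26 is day 182. Each may move by ±3 days.

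| Group | Nominal | Shortest | Longest | Short of 28 days |
|---|---|---|---|---|
| Dosed to week 24 | 182 − 168 = 14 | 179 − 171 = 8 | 185 − 165 = 20 | 14 (8 to 20) |
| Early terminators who exit | 14 | 14 − 3 = 11 | 14 + 3 = 17 | 14 (11 to 17) |

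The early-termination range assumes that the general ±3-day window also applies to the exit visit, which the protocol does not say outright. No timing within the windows reaches 28 days in either group.

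**3. Subjects who stop drug but stay in.** Protocol 6.18 says: "Investigator should encourage a subject to remain in the study even if the investigational product administration is stopped". For them V9 can fall well after the last dose. V9 on day 182 gives 28 days if the last dose was by 182 − 28 = day 154, which is week 22. That limit is nominal. If V9 takes place three days early, a subject who stopped on day 154 has 179 − 154 = 25 days. Cover under any permitted V9 timing needs a last dose by 179 − 28 = day 151.

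**4. What covers the remaining days.**
- SAP 9.3 closes AE collection at the last scheduled contact.
- The post-contact text relies on the subject to report and the investigator to judge relatedness. That is passive, filtered reporting.
- Telephone contact appears only as a possible source of such reports. The week 2 and week 18 calls, by contrast, have their own columns in Appendix 1 and their own sections (7.4 and 7.7).
- Protocol 6.16.3 applies once the investigator knows of an event. It does not make anyone ask.

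**The case against.** **The duty stands apart from the visit grid.** The best defence is that 6.16.7 itself imposes the obligation, that its closing sentence has no relatedness filter, and that the same paragraph mentions telephone contact. On that reading the schedule lists visits, and sites must add whatever calls are needed. Part of this stands: the requirement can be read as all-cause, and a site that telephoned at day 28 would comply. It does not resolve the conflict. No call is scheduled or given a window, and SAP 9.3 ends collection at the last scheduled contact in the same section that asks for four weeks.

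**Two weeks may be enough clinically.** Protocol 3.3.2 gives a half-life of 6.5 h, rising to 7.7 h at GFR below 30, without accumulation. At 7.7 h, 14 days is 14 × 24 / 7.7 ≈ 44 half-lives, and even 8 days is 8 × 24 / 7.7 ≈ 25. This stands as an argument for shortening the requirement. It is no argument for keeping a requirement that the schedule misses.

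**Events are followed to resolution.** Protocol 6.16.7 does this for SAEs known at the last contact, and 7.10 for drug-related toxicity that led to removal. This stands, and it limits the gap. It follows events already found; it does not look for new ones.

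**Stronger readings that the documents do not support.** The SAP's treatment-emergent event "is defined as an AE that begins after the first administration of double-blind study medication", and the definition has no end date. A reader might infer that the serious-event and death tables will mix all-cause events up to V9 with selectively reported events after it. That is not shown: SAP 9.3 limits collection to the last scheduled contact, later related SAEs go to the sponsor, and SAP 2.1 leaves detailed SAE follow-up outside this report. A reader might also multiply the missing days by the number randomized to obtain patient-years lost. A range built that way would put every subject at the same window extreme and ignore the follow-up of drug-related toxicity. It would bound unscheduled time and say nothing about the number of events missed.

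**Conclusion.** The conflict is real and lies within both documents. Scheduled contact after the last dose is nominally 14 of the 28 required days, both for subjects dosed to week 24 and for early terminators who exit. For anyone dosed to week 24 the shortfall is at least 8 and at most 20 days under the stated windows. For early terminators it is 11 to 17 days if the same window applies to their exit visit.

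The conclusion assumes that V8 is the last dosing day, as Protocol 5.11 says, and that active monitoring means a planned contact at which SAEs are asked about. Subjects who stop by about week 22 and remain to week 26 are nominally outside it.

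The gap applies to both blinded arms and leaves efficacy, power and type I error untouched. It should be corrected because it concerns a stated safety commitment and the remedy is simple.

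**What to change.** **Preferred: keep four weeks and schedule it.**
1. Add to Protocol Appendix 1 and SAP Table 1 one telephone SAE contact at last dose + 28 days, for any subject with no visit on or after that day. Set the window at 0 to +3 days and exempt the call from the general ±3 days, which would allow it on day 25. Tying the call to the absence of a later visit also covers the subject who stops at week 22 and has an early V9.
2. In Protocol 6.16.7 and SAP 9.3, state: *All SAEs, regardless of cause, are actively solicited and reported under Protocol 6.16.3 until at least 28 days after the last dose.*

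The call would also serve Protocol 6.16.4, which says of pregnancy: "This reporting requirement will continue until 4 weeks after the last investigational product exposure".

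Cost: at most about 300 calls; a maximum subject duration of 32 instead of 30 weeks; a final analysis up to about two weeks later, since Protocol 9.9 and SAP 2.2 wait for follow-up to finish; and a protocol amendment with IRB/IEC approval before use (Protocol 10.2), with the duration in the consent form updated (Protocol 6.2). The call can be made only for subjects not yet past day 28. SAP 13 already refers to outliers in the dataset, so for some subjects that day may have gone by.

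**Alternative: if the sponsor judges two weeks sufficient.** Replace the four-week sentence in both documents with: *All SAEs, regardless of cause, are actively solicited until the last scheduled contact (week 26, or two weeks after the last dose for subjects who terminate early).* The half-life data in Protocol 3.3.2 could be cited as the reason. This adds no contacts, but it also needs an approved amendment, and it openly halves the stated follow-up period.
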